3.2 TRIAL FLOWCHART

A randomised double blind, placebo controlled study of the efficacy of topical menthol for pain relief during topical photodynamic therapy

v.6.0 27/March/2019

3.3 STUDY MATRIX

| ACTIVITY | Day 1 | Day 2 | DAY 8 | Approx. 3 months |
|--|-------|-------|-------|------------------|
| Informed consent | √ | | | |
| Eligibility screening | √ | | | |
| Standard skin preparation for PDT | √ | | | |
| Application of IMP/placebo (remove after 10 minutes) | √ | | | |
| PDT irradiation | √ | | | |
| Pain assessment (visual analogue scores) by subject immediately after PDT - clinic | √ | | | |
| Fluorescence assessment by technician | √ | | | |
| Phototoxicity assessment by technician | √ | | | |
| Pain assessment (visual analogue scores) by subject 3hrs after PDT - home | √ | | | |
| Pain assessment (visual analogue scores) by subject 6 hrs after PDT - home | √ | | | |
| Pain assessment (visual analogue scores) by subject 24 hrs after PDT - home | | √ | | |
| Follow-up phone call by research nurse | | | √ | |
| Assessment of treatment efficacy at 3 months after PDT | | | | √ |
| Patient evaluation of PDT & blinding | | √ | | |

4 STUDY POPULATION

4.1 NUMBER OF PARTICIPANTS

30 patients will be recruited to the study, with a view to 21 completing the study allowing for a 30% drop-out rate at the three month follow-up visit. The study will be performed in one centre and each participant will be in the study for three months.

A randomised double blind, placebo controlled study of the efficacy of topical menthol for pain relief during topical photodynamic therapy

v.6.0 27/March/2019

4.2 INCLUSION CRITERIA

A subject will be eligible for inclusion in this study only if all of the following criteria apply:

1. Adults >18 years. Target population is men or women ≥ 50 years (only post-menopausal women)
2. Presence of actinic keratoses (AK) on the face and scalp involving both right and left comparable sites.
3. Free of significant physical abnormalities (e.g. tattoos, dermatoses) in the potential treatment area that may cause difficulty with examination or final evaluation.
4. Able to understand and adhere to protocol requirements.

4.3 EXCLUSION CRITERIA

1. Unable to give written informed consent.
2. Allergy to menthol, aqueous cream or excipients
3. Participation in a drug trial or other interventional study within 30 days of recruitment to this study
4. Pre-menopausal women, pregnancy, breast feeding, planning to conceive
5. Chronic pain

5 PARTICIPANT SELECTION AND ENROLMENT

5.1 IDENTIFYING PARTICIPANTS

Potential participants with a diagnosis of actinic keratosis (AK) who are referred for PDT will be identified by the chief investigator (CI), a consultant dermatologist via screening referrals and will be invited to participate by letter and a patient information sheet (PIS) will be sent out with the PDT clinic appointment details. Potential participants will also be identified during consultation by a Dermatologist, Specialist Nurse or technologist in the Dermatology or PDT clinics. Patients will be invited to participate in the study and will be given a Participant Information Sheet (PIS), which will include contact details for members of the research team. In the event of the patient not receiving the study PIS in the clinic, one will be sent with their appointment letter for the PDT clinic. All subjects will be given at least 24 hours to read the PIS and have the opportunity to discuss the study and have any questions answered before deciding if they wish to participate in the study. If willing to proceed, written informed consent will be obtained by a Dermatologist or a delegated suitably qualified member of the research team.

5.2 CONSENTING PARTICIPANTS

Where a participant requests to speak with a Dermatologist from the study team the consent process will not be completed until the participant has spoken to the doctor and had all their questions answered to their satisfaction.

5.3 SCREENING FOR ELIGIBILITY

Potential participants with a diagnosis of actinic keratosis (AK) bilaterally affecting face or scalp who are referred for PDT will be identified by the Chief Investigator (CI), a consultant dermatologist, screening referrals and will be invited to participate by letter and a patient information sheet (PIS) will be sent out with the PDT clinic appointment details. Patients will also be identified in the dermatology outpatient or

A randomised double blind, placebo controlled study of the efficacy of topical menthol for pain relief during topical photodynamic therapy

v.6.0 27/March/2019

PDT clinics by either a dermatologist, specialist nurse or technologist and will be provided with details of the study and a PIS. At first visit at the PDT clinic the study will be described in full detail by a PDT study doctor, technologist or clinic nurse and written informed consent will be obtained prior to any study-related activities.

5.4 INELIGIBLE AND NON-RECRUITED PARTICIPANTS

A screening log will be populated and maintained to list reasons for ineligibility and non-recruitment. These patients will then proceed to standard clinical care

5.5 RANDOMISATION

5.5.1 Randomisation

Randomisation will be to left or right side within each individual as we cannot consider pain experiences on right vs. left within an individual as being independent. We want to compare pain immediately after PDT illumination (time-point of most interest) and, as another way of comparing between the interventions "pain experience over-time" (while trying to reduce the multiple comparisons "problem"), to compare within-subjects Areas Under the Curve of pain over time.

Patients will be randomly allocated to either active or placebo treatment to right or left side using a computer-generated block randomisation sequence, which will also include randomisation as to which side will be treated first. The randomisation code will be generated by Tayside Pharmaceuticals and will be concealed from study investigators.

5.5.2 Treatment Allocation

Patients will be allocated treatment to both right side and left side e.g. right side to receive treatment A; left side to receive treatment B. Patients should be unable to distinguish treatments by smell as menthol has a strong smell, which will likely permeate the air around the patient. In addition, menthol vapour will be present in the room so that there is an overall menthol smell, which will be difficult to localise.

5.5.3 Blinding and Emergency Unblinding Procedures

Those assessing patients (Consultant Dermatologist, study technologist or research nurse) will not be aware of which side has received which intervention. It is possible that all patients (from sensation [cooling] of menthol) might not remain fully blinded. Patients will be instructed not to tell those assessing them if they suspect they know which intervention is applied to each side. After treatment, patients will be asked to provide an opinion as to which treatment was applied to each side to allow assessment as to how complete patient blinding was.

Given the nature of the study, it is very unlikely that unblinding will be required. If required, it will be conducted by a PBU member of staff unconnected to the trial.

5.5.4 Withdrawal procedures

Although a participant is not obliged to give reason(s) for withdrawing prematurely, if the participant appears lost to follow up, the CI will make a **reasonable** effort to ascertain the reason(s), while fully respecting the individual's rights, and will demonstrate that everything possible was done in an attempt to find any participant lost to follow-up. Those lost to follow-up or withdrawn will be identified and a

A randomised double blind, placebo controlled study of the efficacy of topical menthol for pain relief during topical photodynamic therapy

v.6.0 27/March/2019

descriptive analysis of them provided, including the reasons for their loss and its relationship to treatment and outcome.

6 INVESTIGATIONAL MEDICINAL PRODUCT

6.1 STUDY DRUGS/IMPS

6.1.1 Study drug identification

Active IMP is formulated into a cream and supplied as 1g in a 2ml syringe for topical administration.

Composition of Active IMP - Levomenthol 5% Cream

| Component | Reference | Amount |
|------------------|---------------------|---|
| Menthol | Ph Eur | 50mg (5% w/w) |
| Aqueous Cream | BP PL 04917/0057 | to 1g (50mg menthol + 950mg aqueous cream) |

Placebo is provided as a cream (1g in a 2ml syringe) for topical administration.

Composition of placebo cream - Aqueous Cream BP.

| Component | Reference | Amount |
|------------------|---------------------|---------------|
| Aqueous Cream | BP PL 04917/0057 | 1g (100%) |

6.1.2 Study IMP Manufacturer

The investigational drug substance is Menthol 5% in Aqueous Cream. This product is manufactured by Tayside Pharmaceuticals, Ninewells Hospital & Medical School, [name], MIA (IMP) 14076 (see IMPD).

The placebo is Aqueous Cream BP, which is a licensed product, PL 04917/0057

6.1.3 Marketing authorisation holder

Tayside Pharmaceuticals MIA (IMP) 14076

6.1.4 Labelling and Packaging

Study IMPs will be packaged and labelled by Tayside Pharmaceuticals.

6.1.5 Storage

Study IMPs will be released by Tayside Pharmaceuticals to NHS Tayside Pharmacy who will supply them to the PBU. IMPs will be stored in a local PBU storage area which will be audited prior to use by the NHS Tayside Clinical Trials Pharmacist. Temperature control logs will be maintained.

6.1.6 IMP Safety Information

The simplified IMPD will be held in the Pharmacy Site File (PSF) and in the Trial Master File (TMF). No adverse effects are expected. A minor cooling or tingling

A randomised double blind, placebo controlled study of the efficacy of topical menthol for pain relief during topical photodynamic therapy

v.6.0 27/March/2019

sensation may be expected with IMP contact with skin. Contact with eyes or mucosal surfaces will be avoided as these are not within the study treatment sites.

6.1.7 Accountability procedures

An IMP Accountability Log will be maintained in the TMF.

6.3 DOSING REGIME

IMP will be applied topically by a study technologist or nurse at study Visit 1. After removal of the dressings and surplus Ameluz[®] gel, the active treatment (menthol 5% in aqueous cream) or placebo (aqueous cream) will be applied to right/left side according to randomisation. Ten minutes later any excess cream will be wiped off and irradiation will commence using a standard red light LED (37.5 J/cm², irradiance 80 mW/cm²), with the randomisation to account for which side will be treated first. Menthol vapour will be in the room in order to mask the vapour of the IMP and to aid with ensuring blinding of both patient and assessor (research nurse or another technologist).

6.4 DOSE CHANGES

No planned dose changes in IMPs

6.5 PARTICIPANT COMPLIANCE

As both IMPs will be applied topically by a study technologist at study Visit 1, there will be no requirement to monitor participant compliance as this will not be relevant.

6.6 OVERDOSE

No risk of overdose

6.7 OTHER MEDICATIONS

6.7.1 Permitted medications

Usual medications are permitted except for menthol preparations used on the treatment day.

6.7.2 Prohibited medications

Menthol preparations used on the treatment day

6.7.3 Concomitant Medications

All usual medications will be permitted except for menthol preparations. Concomitant medications will be logged in the Case Report Form (CRF).

7 STUDY ASSESSMENTS

7.1 STUDY ASSESSMENTS

As detailed above – pain, fluorescence, phototoxicity, efficacy and patient evaluation will be assessed.

7.2 SAFETY ASSESSMENTS

Pain and phototoxicity will be assessed by per protocol and intention to treat analyses

A randomised double blind, placebo controlled study of the efficacy of topical menthol for pain relief during topical photodynamic therapy

v.6.0 27/March/2019

8 DATA COLLECTION & MANAGEMENT

8.1 DATA COLLECTION

Data will be collected in the CRF and appropriate clinical information will also be recorded in patient notes. Both patient notes and CRF will act as source data.

8.2 DATA MANAGEMENT SYSTEM

The data management system will be Excel. The study system will be based on the protocol and CRF. The CRF will not collect more information than is required to meet the aims of the study and to ensure the eligibility and safety of the participant. Data collection and validation will be carried out as described in TASC SOP on Excel in CTIMPs.

9 STATISTICS AND DATA ANALYSIS

9.1 SAMPLE SIZE CALCULATION

We were not able to obtain variance for within-subjects pain differences from similar studies. An assessment of pain experience with PDT in our unit found a standard deviation of between subjects VAS pain score of 2.7cm. Rounding this up to 3cm and conservatively estimating that within-subject's pain score SD will be two-thirds of this (2cm) then we estimated that 21 subjects should give us 90% power to detect a mean difference in VAS scores of 1.5 cm as significant at the 5% level. To allow for dropouts, assuming dropout rate by 3 months of up to 30%, we will recruit 30 subjects.

9.2 PROPOSED ANALYSES

The main analysis will be the difference between within-subject pain using appropriate paired methods (paired Student's t-test if assumptions met). The difference will be expressed with 95% confidence interval. VAS scores immediately after PDT and the areas under the curve for pain scores plotted over each of the time points will be assessed. Within subject comparisons of fluorescence, phototoxicity, efficacy and patient evaluation will be secondary outcome measures, using paired statistical analyses.

Amendment

Since the original concept and set up of the study, there have been changes in the practice of PDT for AKs on the face and scalp, with low illuminance daylight PDT now favoured when practicable because this form of PDT is less painful than conventional PDT. Therefore, we will perform (statistical analysis by someone not involved in patient treatments and assessments, to ensure blinding) an interim analysis. With the same assumptions as before with a power of 90% we expect to detect a difference (at alpha = 0.1 level, two tailed testing) of 3 cm or more (on VAS) in pain between groups with 9 subjects should such a difference exist. We will therefore recruit a minimum of 9 participants and if on this interim analysis such a difference is detected then the study will be continued as originally planned in order to determine whether the difference can be detected at alpha = 0.05 level of significance, unless the dermatologist analysing the data advises stopping early as a greater difference already detected. If it seems unlikely that there will be a difference of ≥ 3 cm in pain

A randomised double blind, placebo controlled study of the efficacy of topical menthol for pain relief during topical photodynamic therapy

v.6.0 27/March/2019

on VAS based on this interim analysis, then (with the changes in use of PDT for AKs on face and scalp) the data analyst will advise stopping the study.

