3 STUDY DESIGN

3.1 STUDY DESCRIPTION

This protocol describes a prospective, single site, randomised, double blind placebo controlled study to assess the efficacy of menthol in aqueous cream for PDT-induced pain. Each subject will act as their own control. Potential participants with a diagnosis of actinic keratosis (AK) bilaterally affecting face or scalp who are referred for PDT will be identified by the Chief Investigator (CI), a consultant dermatologist, screening referrals and will be invited to participate by letter and a patient information sheet (PIS) will be sent out with the PDT clinic appointment details. Patients will also be identified in the dermatology outpatient or PDT clinics by either a dermatologist, specialist nurse or technologist and will be provided with details of the study and a PIS. At first visit at the PDT clinic the study will be described in full detail by a PDT study doctor, technologist or clinic nurse and written informed consent will be obtained prior to any study-related activities. Computer-generated block randomisation of the active/placebo to right or left sides and which side will be treated first will be undertaken by Tayside Pharmaceuticals. Patients will then receive their randomised treatment and this will also be undertaken by the Photobiology Technician or nurse as is the normal clinical practice in the PDT Unit.

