A study clinician, technologist or nurse will obtain a medical history and the areas for treatment will be examined, the study fields will be marked out, lesions counted and the fields mapped and photographed. The maximal diameter of each comparable field will be 5x10cm. Topical PDT will be undertaken using the standard Ameluz[®] PDT regime (11). In brief, any hyperkeratotic areas will be surface prepared using a disposable ring curette (Stiefel[™]), without the need for local anaesthesia. Ameluz[®] gel will be thinly applied to both comparative fields, left to dry and occluded for three hours with Tegaderm and Mepore dressings. After removal of the dressings and surplus gel, the active treatment (menthol 5% in aqueous cream) or placebo (aqueous cream) will be applied to right/left side according to randomisation. The IMPD/placebo will be provided as 1g in 2mL syringes, applied to the maximum field size field of 5x10cm or pro-rata to smaller field sizes. Ten minutes later any excess cream will be wiped off and irradiation will commence (LED 37.5 J/cm², irradiance approximately 80 mW/cm²), with the randomisation to account for which side will be treated first. Menthol vapour will be in the room in order to mask the vapour of the IMP and to aid with ensuring blinding of both patient and assessor (research nurse or another technologist).

Assessments

Fluorescence will be examined using a semi-quantitative scoring system (0=none; 1=minimal; 2=moderate; 3=strong) after 3 h of Ameluz application and after menthol/placebo application.

Pain scores will be recorded by the patient immediately after irradiation (as recall of maximal pain experienced during irradiation) and at 3, 6 and 24 h after irradiation

A randomised double blind, placebo controlled study of the efficacy of topical menthol for pain relief during topical photodynamic therapy

[figure not shown]
v.6.0 27/March/2019

using a VAS score of 0-10cm at each time-point. The study technologist or research nurse will be present at the time of the first pain score but patients will fill in the VAS scores themselves at home for the 3, 6 and 24 h time-points and send these back to the PDT clinic by stamped addressed envelope. A study nurse will contact the patient by phone at one week, to ask about any adverse effects and to check that the VAS scores are returned.

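### Section 9.2's paired t-test has no term for the randomised irradiation order; the test is valid, and adding the term to the final analysis is a cheap, conditional gain in precision

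*Combined protocol and SAP*

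**What the plan says.** Section 3.1 describes "Computer-generated block randomisation of the active/placebo to right or left sides and which side will be treated first", and section 5.5.1 repeats that there is one block sequence, "which will also include randomisation as to which side will be treated first". Sections 3.1 and 6.3 say that irradiation starts "with the randomisation to account for which side will be treated first".

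For the analysis, section 9.2 says "The main analysis will be the difference between within-subject pain using appropriate paired methods". It names the paired Student's t-test if assumptions are met and asks for a 95% confidence interval. It applies this to the VAS immediately after PDT and to the area under the pain curve. No section names irradiation order as a model term, a stratum or a sensitivity analysis.

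Section 5.5.1 singles out the immediate score as the time point of most interest. The study matrix (section 3.3) lists it as "Pain assessment (visual analogue scores) by subject immediately after PDT - clinic", on Day 1. Section 4.1 plans 30 recruits "with a view to 21 completing the study allowing for a 30% drop-out rate at the three month follow-up visit". On variability, section 9.1 states: "We were not able to obtain variance for within-subjects pain differences from similar studies". It adopts 2 cm instead.

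**The concern.** The two fields are irradiated one after the other, so each patient has a first and a second exposure. If the second hurts more or less than the first by g, each menthol-minus-placebo difference is shifted by +g when menthol was second and by -g when it was first. Randomising order stops this from biasing the mean. It does not remove the shift from the spread of the differences, which is what the plain t-test uses as error. A signed-rank test, if used because the t-test assumptions fail, has the same feature.

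A non-zero g is plausible. At 37.5 J/cm² and 80 mW/cm² (section 6.3), one exposure lasts 37.5 / 0.080 = 469 s, about 7.8 minutes. If both creams go on together, the second field waits about 18 minutes instead of 10. The documents do not say whether application is staggered.

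What is at stake is the width of the interval and, if g is large, some power. Validity is not in question.

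**Working it through.** **1. The plan's own figure.** Inputs from section 9.1: difference 1.5 cm, SD 2 cm, 5% level, 90% power. Taking 2 cm as the SD of the paired difference and testing two-sided, noncentral-t power is 88.9% at n = 20 and 90.5% at n = 21. So 21 is reproduced, and 21 / 0.7 = 30 gives the recruitment target.

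**2. Model.** For patient i, D = τ + g·s + e. Here D is menthol minus placebo, s = +1 if menthol was second and -1 if first, and e has SD σ. With order split evenly:

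- plain paired test: expected sample variance of D is σ² + g²·n/(n-1), on n-1 df;
- order-adjusted: σ², on n-2 df.

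**3. CI width, n = 30, balanced, σ = 2 cm (assumed to be the SD within order groups).** The t quantiles are 2.0452 (29 df) and 2.0484 (28 df).

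- Adjusted: 2 × 2.0484 × 2 / √30 = 1.496 cm.
- Plain, g = 0.5: 2 × 2.0452 × √(4 + 0.25 × 30/29) / √30 = 1.541 cm; ratio 1.03.
- Plain, g = 1: 2 × 2.0452 × √(4 + 30/29) / √30 = 1.676 cm; ratio 1.12.

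Simulated mean widths at g = 1 are 1.66 and 1.48 cm, the same ratio.

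**4. Power (simulation, 100,000 trials per cell, effect 1.5 cm, two-sided 5%, σ = 2 cm).** g is an assumed range. Section 5.5.1 does not say whether the blocks balance order, so both cases are shown, as plain / adjusted.

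| n | Order | g = 0 | g = 0.5 | g = 1 |
|---|---|---|---|---|
| 30 | balanced | 97.8 / 97.8% | 97.4 / 97.7% | 96.0 / 97.7% |
| 30 | by chance | 97.9 / 97.4% | 97.1 / 97.4% | 94.5 / 97.4% |
| 21 | balanced (10:11) | 90.5 / 90.3% | 89.2 / 90.2% | 85.2 / 90.1% |
| 21 | by chance | 90.5 / 88.6% | 88.7 / 88.9% | 83.4 / 88.7% |

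The immediate score is taken in clinic on Day 1, while the 30% loss is placed at three months. The n = 30 rows are therefore the relevant ones, and n = 21 is a lower bound.

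**5. Type I error of the plain test, n = 30.** Balanced: 5.1%, 4.3% and 2.8% at g = 0, 0.5 and 1. By chance: 5.0% throughout. Adjusted: 4.9–5.1%.

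**6. Break-even g.** Balanced: about 0.1 cm (n = 30) or 0.2 cm (n = 21). By chance: about 0.4 or 0.5 cm. Below these values the term loses slightly.

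**7. If the 2 cm already contains order variation.** Then σ = √(4 - g²) and no planned power is lost. At n = 30, balanced, the adjusted CI is 3% narrower at g = 0.5 and 14% narrower at g = 1.

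**8. AUC.** Trapezoid weights over 0, 3, 6 and 24 h are 1.5, 3, 10.5 and 9, totalling 24. The immediate score carries 1.5/24 = 6%, and the 6 h and 24 h scores carry 19.5/24 = 81%. A 1 cm order effect confined to the irradiation moves the time-averaged AUC by about 0.06 cm.

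**9. Interim, n = 9 (3 cm, alpha 0.1, g = 0).** Plain power is 99.3%; adjusted is 99.1% at a 4:5 split and 95.6% at 2:7. With order by chance, the adjusted interval is on average about 9% wider. At 1:8 a rank-sum test cannot go below p = 2/9 = 0.22, and at 0:9 the adjusted effect cannot be estimated. By coin-toss, 1:8 or worse has probability 20/512 = 3.9%.

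**The case against.** The strongest reply is that nothing is wrong. Order is dealt with by randomising it, the planned wording leaves room for an order term, and the benefit depends on a g that no section estimates. The visible gains need g near 1 cm, two-thirds of the target effect. At 0.5 cm the gain is about 3% of CI width, and at n = 30 unadjusted power is still at least 94.5% at g = 1. All of this stands. It is why the point is an improvement in precision and no more.

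Four stronger readings are tempting, and the documents support none of them:

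- **Bias or excess false positives.** A reader might infer these from the missing term. Random order prevents bias, and the error rate is at or below nominal.
- **A gain without cost.** The cost is negligible only if order is close to balanced. Section 5.5.1 promises blocks but gives no block structure, and with order left to chance a small g makes the term a slight loss.
- **The same gain for the AUC.** That needs an order effect lasting hours, which no section suggests.
- **Use at every look.** At nine patients the term costs more and may not be estimable, although blocking may make extreme splits unlikely.

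What survives is that the trial randomises this factor, so it is available for analysis, and that section 9.2 leaves its use to be decided later, possibly with the data in view.

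**Conclusion.** The point holds as a cheap improvement, not as an error in the plan. For the final immediate-VAS analysis with 30 patients, balanced order and a within-order SD of 2 cm, leaving order out widens the 95% CI by about 12% at g = 1 cm (power 96% against 98%). At g = 0.5 cm the CI is about 3% wider and power is almost unchanged. If the blocks balance order and g is not zero, the plain test is also conservative, so its interval over-covers.

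These sizes rest on an assumed g, on reading 2 cm as the SD within order groups, and on nearly all recruits giving the Day 1 score. An order main effect does not address an order-by-treatment interaction, such as carry-over or a different cream-to-light interval.

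**What to change.** Add to section 9.2:

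- The final analysis of the menthol-minus-placebo difference in immediate VAS will use a linear model with irradiation order (menthol first = -1, menthol second = +1) as a fixed effect. The intercept will be reported with its 95% CI.
- If the t-test assumptions are not met, first-minus-second differences will be compared between menthol-first and menthol-second patients by a Wilcoxon rank-sum test. Half the Hodges-Lehmann shift will be reported with its 95% CI. (The shift between these groups is 2τ and g cancels, so half of it estimates τ.)
- The nine-patient interim will keep the plain paired test. Order adjustment of the AUC is optional.

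The cost is a few sentences, with no new data or patients, because order is already in the randomisation list. If there is no order effect, the linear model gives up under 0.1 power points at n = 30 and about 0.2 at n = 21 with balanced order, or about 0.5 and 2 points if order is left to chance. The rank version gives up under 1 point with balanced order, or about 1 and 3 points by chance. Stating whether the blocks balance order would settle which of these costs applies.

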Most patients receiving PDT experience pain during irradiation. In Dundee, 16% of 4717 PDT treatments were associated with severe pain [4]. This limits successful and effective delivery of PDT and negatively impacts on the patient's experience of treatment. Unsurprisingly, given the nature of pain transmission, PDT is most painful in patients when performed on highly innervated skin such as the face and scalp [5, 13]. Interestingly, higher pain levels are experienced during PDT for AK and psoriasis than for basal cell carcinoma [13, 14], perhaps implicating neuromodulatory factors released from specific cell types. Characteristics of irradiation (emission spectrum and irradiance) appear to influence the perception of pain. Red light produces more pain than violet light and pain appears to correlate with the rate of photobleaching of PpIX [15, 16]. Reduction of irradiance may reduce pain but greatly increases treatment times [6, 7]. Other options for pain relief are limited as conventional non-invasive methods, such as topical analgesia with morphine or local anaesthetics are not significantly effective [5, 17, 18]. Local anaesthetic nerve block results in effective pain reduction [19] but is invasive, not feasible at all body sites and there may be risk of toxicity. Cooling is associated with slight reduction in PDT-induced pain [20], although there are concerns that this may reduce the efficacy of PDT [21].

Mechanisms of PDT pain

A randomised double blind, placebo controlled study of the efficacy of topical menthol for pain relief during topical photodynamic therapy

v.6.0 27/March/2019

Little is known about the mechanism(s) of PDT-induced pain. At the time of writing a literature search using the terms “pain and photodynamic therapy” yielded 423 publications, although most relate to the prevalence of PDT-pain and the limited success of treatment. Inhibition of PDT-induced pain by nerve block [19] implicates classical modes of pain transmission in which voltage activated sodium channels (VASCs) are activated leading to action potentials in primary afferent fibres stimulating ascending pain pathways in the spinal cord, thalamus and cortex [22]. PDT pain is described as a burning sensation. Furthermore, demonstrations that cooling reduces PDT pain may implicate heat-sensitive nociceptors. The transient receptor potential (TRP) family of ion channels senses heat, among other noxious stimuli including the pungent vanilloid capsaicin [23].

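### The paired pain analysis is valid, but it leaves out the randomised irradiation order and the pre-cream fluorescence difference, which one pre-specified sentence could use at the final analysis

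*Combined protocol and SAP*

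**What the plan says.** Section 9.2 (Proposed Analyses) defines the pain analysis: "The main analysis will be the difference between within-subject pain using appropriate paired methods", qualified as "paired Student's t-test if assumptions met", with a 95% confidence interval. It covers the score immediately after PDT and the area under the curve. No covariate is named. Fluorescence appears in 9.2 only as a secondary outcome, and lesion count does not appear.

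Section 3.1 describes what is recorded before the study cream can act. When the fields are marked out, staff have "lesions counted and the fields mapped and photographed". Fluorescence is scored 0 to 3 "after 3 h of Ameluz application and after menthol/placebo application", which gives one score before the study cream and one after it.

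Sections 3.1 and 5.5.1 say that the block randomisation covers both which side receives menthol and which side is irradiated first.

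Section 1.1 gives a qualitative reason to connect PpIX with pain: "pain appears to correlate with the rate of photobleaching of PpIX".

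Section 9.1 claims that "21 subjects should give us 90% power to detect a mean difference in VAS scores of 1.5 cm as significant at the 5% level". It uses an assumed SD of 2 cm and concedes: "We were not able to obtain variance for within-subjects pain differences from similar studies".

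**The concern.** Pairing removes differences between patients. It does not remove differences between the two fields of one patient, or any effect of being irradiated first or second. Section 4.2 requires comparable right and left sites, but nothing requires equal lesion load or equal PpIX. If the side with more PpIX hurts more, or the second irradiation feels different from the first, that variation stays in the paired difference and widens the confidence interval.

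One of these factors is randomised by design. The other is measured before the study cream. Both can enter the model without biasing the treatment effect. At stake is precision in a small trial whose SD is a guess. A second risk is that, without a pre-specified choice, a covariate is picked after the data are seen, or the post-cream fluorescence score is used by mistake.

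**Working it through.** **Inputs.** From 9.1: 21 completers, effect 1.5 cm, 5% level (taken as two-sided), SD 2 cm (taken as the SD of the paired difference). From 9.2: interim at 9 patients, 3 cm, alpha 0.10 two-tailed, 90% power. Not in the documents, so assumed over a range: the correlation ρ between the side difference in pre-cream fluorescence and the side difference in pain, from 0 to 0.5. Order is assumed unrelated to pain.

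**1. The plan's own figure.** The noncentrality is 1.5/(2/√21) = 3.44 on 20 df. Power is 90.5%, so the 21 in 9.1 reproduces.

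**2. Why a second SD is shown.** The interim claim in 9.2 is said to rest on the same assumptions. With 9 patients and 3 cm at alpha 0.10, power is 99.3% if the SD of differences is 2 cm and 89.5% if it is 2 × √2 = 2.83 cm. The stated 90% therefore fits 2.83 cm. At that SD, 21 patients have 63.8% power for 1.5 cm.

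**3. The adjusted model.** Regress the menthol-minus-placebo VAS difference on order (+1 if the menthol side is irradiated first, -1 if second) and on the menthol-minus-placebo difference in pre-cream fluorescence, uncentred. The intercept is the treatment effect at equal fluorescence, averaged over the two orders. Residual df are 21 - 3 = 18.

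With order balanced, the variance relative to the unadjusted mean is about (1 - ρ²)(1 + 1/(n - 4)) = (1 - ρ²) × 1.059. Power uses noncentrality 1.5/(SD × √factor/√21) on 18 df. Simulation agrees to within about one point.

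| ρ (assumed) | Variance factor | Power, SD 2 cm | Power, SD 2.83 cm |
|---|---|---|---|
| Unadjusted | 1 | 90.5% | 64% |
| 0 | 1.059 | 88 to 89% | 61% |
| 0.3 | 0.91 × 1.059 = 0.964 | 91% | 64 to 65% |
| 0.4 | 0.84 × 1.059 = 0.889 | 93% | 68 to 69% |
| 0.5 | 0.75 × 1.059 = 0.794 | 95% | 73% |

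The factor equals 1 at ρ = √(1 - 1/1.059) ≈ 0.24. The two lost df push the break-even in power slightly higher, but still below 0.3.

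**4. If order is not balanced.** The factor becomes (1 - ρ²)(1 + 2/17) = (1 - ρ²) × 1.118. At SD 2 cm, power is about 87% at ρ = 0, 90% at 0.3, 92% at 0.4 and 94% at 0.5. The loss at ρ = 0 is then up to about 4 points, and the break-even moves to about 0.34.

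**5. Validity.** In simulation at 21 patients, the type I error of the adjusted test stayed at about 5%.

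**6. The interim.** At n = 9, two general covariates inflate the variance by 1 + 2/(9 - 4) = 1.40 before any gain. They need a joint R² of about 0.30 to break even.

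**7. If more patients contribute.** The 30% dropout in 9.1 is by three months (30 × 0.7 = 21), whereas the immediate pain score is taken on day 1. With 30 patients, unadjusted power is 97.8% at SD 2 cm and 80.2% at 2.83 cm.

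**The case against.** The strongest case against is that the planned test has no error to correct. Side is randomised, so the paired t-test is unbiased, and its standard error already allows for chance imbalance between sides. That stands.

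The gain rests on a correlation found nowhere in the documents. The sentence in 1.1 concerns the rate of photobleaching during irradiation, not a four-level score taken beforehand. Both fields receive the same gel for the same time on comparable sites, so many side differences may be zero and the correlation may be weak. That also stands, and it is why a loss at zero correlation is shown. Ties do not invalidate the model: for a given correlation, simulation with 50 to 70% ties left power almost unchanged.

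A further objection is that two terms cost more than one and lose power even at a correlation of 0.3. That holds only if order is left unbalanced. Sections 3.1 and 5.5.1 describe block randomisation that includes order. If the blocks balance it, the order term alone costs almost nothing. The block structure is not given, so balance remains an assumption.

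Finally, the data may not be there. Only 3.1 clearly gives a separate pre-cream score. The opening summary and 2.1.2 place the assessment after cream application and before irradiation, 2.2.2 places it after Ameluz and IMP, and the matrix in 3.3 has one fluorescence row and no row for lesion counts. Section 3.1 does not say outright that counts are kept by side. This stands and must be settled first.

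**Conclusion.** This is an inexpensive improvement with a known downside. It does not correct a defect. At 21 patients and an SD of 2 cm, adjustment moves power from 90.5% to between about 88% (no relation) and 95% (correlation 0.5). At 2.83 cm it moves from 64% to between about 61% and 73%. The downside is about 2 to 3 points of power if neither term relates to pain, or up to about 4 if order is unbalanced. If up to 30 patients give day-1 pain scores and the SD is 2 cm, there is little left to gain.

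A reader might infer that the unadjusted test is biased, or that the extra precision costs nothing. The documents support neither: randomisation of side protects the estimate, and the degrees of freedom are a real cost. Nor do they show that pre-cream fluorescence predicts pain. They only make it plausible.

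**What to change.** 1. Confirm that the case report form records the pre-cream fluorescence score, and the lesion count, separately for each side. Align the summary, 2.1.2, 2.2.2 and 3.3 with the timing in 3.1.
2. Add to 9.2, for the final analysis only: the treatment effect is the intercept, with 95% confidence interval, of a linear model of the menthol-minus-placebo VAS difference on irradiation order (coded +1/-1 by whether the menthol side is irradiated first) and the menthol-minus-placebo difference in pre-cream fluorescence, uncentred. The plain paired t-test is reported beside it.
3. State that the 9-patient interim uses the paired t-test, that post-cream fluorescence is not a covariate because the study cream could affect it, and that the lesion-count difference is used in a sensitivity analysis only.

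The cost is a few lines of text, fixed before unblinding, and two degrees of freedom. No new data are needed if step 1 confirms that the scores are held by side. If the pre-cream score is not held by side, the fluorescence term cannot be used.
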